5.8 Missing Dates

In analysis of AEs and medication, a complete date will be established in order to identify AEs or medication as occurring during treatment or not. For handling partially reported onset/start and outcome/end dates for AEs or medication the following algorithms are applied:

- AEs:
 - Missing onset day, but month and year present:
 - If baseline visit occurred in the same month and year as the occurrence of the AE, then the onset day of the event is assigned to the date of baseline visit.
 - Otherwise, the onset day is set to the first day of the month (e.g., XX-Sep-2020 is considered as 01-Sep-2020).
 - Missing onset day and month, but year present:
 - If baseline visit occurred in the same year as the occurrence of the AE, then the onset date of the event is assigned to the date of baseline visit.
 - Otherwise, the onset day and month is set to 01 January (e.g., XX-XXX-2020 is considered as 01-Jan-2020).
 - Missing outcome day, but month and year present:
 - The day is set to the last day of the month (e.g., XX-Sep-2020 is considered as 30-Sep-2020).
 - Missing outcome day and month, but year present:
 - The outcome day and month is set to 31 December (e.g., XX-XXX-2020 is considered as 31-Dec-2020).
- Medications:
 - Missing start day, but month and year present:
 - If baseline visit occurred in the same month and year as the occurrence of the medication, then the start day of the medication is assigned to the date of baseline visit. Otherwise, the start day is set to the first day of the month (e.g., XX-Sep-2020 is considered as 01-Sep-2020).
 - Missing start day and month, but year present:
 - If baseline visit occurred in the same month in the same year as the occurrence of the medication, then the start date of the medication is assigned to the date of baseline visit.
 - Otherwise, the start day and month is set to 01 January (e.g., XX-XXX-2020 is considered as 01-Jan-2020).
 - Missing stop day, but month and year present:
 - The day is set to the last day of the month (e.g., XX-Sep-2020 is considered as 30-Sep-2020).
 - Missing stop day and month, but year present:

- The stop day and month is set to 31 December (e.g., XX-XXX-2020 is considered as 31-Dec-2020).
- Date of RA diagnosis:
 - Missing day, but month and year present:
 - Date is set to the first day of the month (e.g., XX-Sep-2010 is considered as 01-Sep-2010).
 - Missing day and month, but year present:
 - Date is set to 01 January (e.g., XX-XXX-2010 is considered as 01-Jan-2010)
- Week 12 visit:
 - If the Week 12 visit date is missing (e.g., the subject missed the Week 12 assessment but is still participating in the study), the Week 12 visit date will be set to the date that subject's MicroRegulator was re-registered for open-label, long-term follow-up

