Baseline	Information and values collected during Screening. The RA disease activity assessments that serve as the baseline assessments used for determination of the primary and key secondary efficacy endpoints must be performed on the day of informed consent.
CDAI	
The CDAI score is based on 4 items:
 
 • TJC28 • SJC28

Term	Definition
	
 SGA EGA 
The CDAI score is calculated as follows and ranges from 0 to 76:
 
 CDAI = TJC28 + SJC28 + SGA + EGA 
The CDAI score corresponds to the current RA activity:
 
 0 to \leq 2.8 Remission >2.8 to \leq 10 Low disease activity (LDA) >10 to \leq 22 Moderate disease activity > 22 High disease activity 
The MCID is a score reduction by 12 if starting in high activity, 6 if starting in moderate activity, and 1 if starting in low activity.

Control to Open Label (COL) population	Control subjects from ITT population who received non-active (sham) stimulation through Week 12, switched to active stimulation after completing Week 12 assessments, continued to receive active stimulation during open-label follow-up, and for whom follow-up data are available.
Crossover	The process of switching from an initially assigned treatment to the other treatment being studied.
DAS28-CRP	
The DAS28-CRP score is a composite index providing a measure of disease activity, comprising:
 
 TJC28 SJC28 SGA hsCRP (mg/L) 
A total score ranges from 0 to 10 and is computed as follows:
 $\text{DAS28-CRP} = 0.56 * \text{sqrt}(\text{TJC28}) + 0.28 * \text{sqrt}(\text{SJC28}) + 0.36 * \ln(\text{CRP}+1) + 0.014 * \text{SGA} + 0.96$ 
The DAS28-CRP score corresponds to the current RA activity:
 
 0 to $<$ 2.6 Remission 2.6 to $<$ 3.2 LDA 3.2 to \leq 5.1 Moderate activity > 5.1 High activity 
A DAS28-CRP score reduction by 1.2 represents the MCID.

Day 0 (randomization, initiation of stimulation)	
Scheduled study visit occurring 14 to 21 days after Implant Procedure during which subjects undergo the following study procedures in the order specified:
 
 Day 0 assessments Randomization Initiation of stimulation 
Subjects must receive final surgical clearance with an approval to initiate study treatment before proceeding to the Day 0 visit.

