5.3 Baseline

Information and RA disease activity assessments collected during Screening on the day of informed consent will be used to confirm initial eligibility and as the baseline assessments for determination of the primary and key secondary efficacy endpoints (**Table 5**).

Baseline assessments for the exploratory endpoints (e.g., EQ-5D-5L, SF-36, RAMRIS, biomarkers) will be collected during Screening.

Table 5: RA Disease Activity Assessments to Be Collected on the Day of Informed Consent and Used as the Baseline Assessments for Determination of the Primary and Key Secondary Efficacy Endpoints

Endpoint	HAQ-DI	SGA	Subject Pain	TJC28	SJC28	EGA	hsCRP
Primary							
ACR20 response	Y	Y	Y	Y	Y	Y	Y
Key Secondary Adjusted for Multiplicity							
ACR20 response from Day 0	Y	Y	Y	Y	Y	Y	Y
DAS28-CRP good/moderate EULAR response	--	Y	--	Y	Y	--	Y
DAS28-CRP response (MCID)	--	Y	--	Y	Y	--	Y
HAQ-DI response (MCID)	Y	--	--	--	--	--	--

Abbreviations: ACR, American College of Rheumatology; CRP, C-reactive protein; DAS, Disease Activity Score; EGA, evaluator's global assessment; EULAR, European League Against Rheumatism; HAQ-DI, Health Assessment Questionnaire Disability Index; hsCRP, high sensitivity CRP; SGA, subject's global assessment; TJC, tender joint count; SJC, swollen joint count; Y, yes.

Note: All response rates are at Week 12 based on change from baseline at the time of informed consent, unless stated otherwise.

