12 APPENDICES

Appendix A: Schedule of Assessments

Assessment	Informed Consent & Screening (Baseline)	Enrollment & Implant Procedure (≤ 30 d post-Informed Consent)	Post-Surgical Clearance (14-21d post-Implant Procedure)	Day 0 (Randomization & Initiation of Stimulation) (14-21d post-)	Titration 1 (7 ± 2 d2)	Titration 2 (14 ± 2 d2)	Titration 3 (21 ± 2 d2)	Week 4 (28 ± 3 d2)	Week 8 (56 ± 5 d2)	Week 12 (Primary Endpoint & One-way Crossover) (84 ± 7 d2)
Informed consent	X*									
Vital signs	X*			X						X
Physical exam and medical history	X*									
Pregnancy test (childbearing female)	X*	X	X	X	X	X	X	X	X	X
RA disease activity assessments ¹	X*			X				X	X	X
RA prior and current medication	X*									
Energizer fit test	X*									
SF-36 & EQ-5D-5L questionnaires	X			X				X	X	X
Blood collection (RF, ACPA, eGFR)	X									
Blood collection (CBC, biomarkers)	X			X				X	X	X
Hand MRI	X									X
12-lead ECG	X									X
X-ray cervical spine	X									
Surgical clearance	X		X							
Implant procedure in operating room		X								
Randomization				X						
Subject training on the use of Energizer				X						
Device check & dose titration				X	X	X				X ³
Device check & dose adjustment if needed								X	X	
Blinding assessment ⁴							X			X
Treatment decision for long-term follow-up										X
Device deficiency reporting		X	X	X	X	X	X	X	X	X
Adverse event reporting	X	X	X	X	X	X	X	X	X	X
Concomitant medication	X	X	X	X	X	X	X	X	X	X

Abbreviations: ACPA, anti-citrullinated protein antibodies; CBC, complete blood count; d, day; EGA, evaluator's global assessment; eGFR: estimated glomerular filtration rate; HAQ-DI, Health Assessment Questionnaire Disability Index; hsCRP, high-sensitivity C-reactive protein; MRI, magnetic resonance imaging; RA, rheumatoid arthritis; RF, rheumatoid factor; SGA, subject's global assessment; SJC, swollen joint count; TJC, tender joint count

* Screening assessments that must be conducted on the day of informed consent to determine subject's initial eligibility and baseline values for the primary and key secondary efficacy endpoints.

¹ RA disease activity assessments include: HAQ-DI, SGA, subject's pain assessment, TJC28, SJC28, EGA, and hsCRP. Subjects must have ≥ 4 TJC28 and ≥ 4 SJC28 at consent to be eligible.

² From Day 0 (randomization).

³ Dose titration is not performed if subject and Co-PI Rheumatologist decide that subject should not receive active stimulation in open-label, long-term follow-up period.

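### SAP 5.8 completes partial adverse-event onset dates without checking the implant date, so some post-implant events could appear as pre-implant in Table 14.1.3.2

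*SAP*

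**What the plan says.** SAP 5.8 (CLP-004) gives the purpose of completing dates: "a complete date will be established in order to identify AEs or medication as occurring during treatment or not". It has two AE onset rules.

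- **Day missing, month and year known.** If the baseline visit is in that month, "then the onset day of the event is assigned to the date of baseline visit". If not: "Otherwise, the onset day is set to the first day of the month".
- **Year only.** If the baseline visit is in that year, "then the onset date of the event is assigned to the date of baseline visit". If not: "Otherwise, the onset day and month is set to 01 January".

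Missing outcome days go to the end of the month or to 31 December. No onset rule refers to the implant date, Day 0 or the outcome date.

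Protocol 3 defines baseline as "Information and values collected during Screening". SAP 5.3 refers to assessments "collected during Screening on the day of informed consent will be used to confirm initial eligibility and as the baseline assessments", and SAP Appendix A labels the consent and Screening column as baseline. Protocol 11.3 puts implant within 30 days after consent.

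The mock-up of Table 14.1.3.2 has one block for AEs before the implant procedure and one for AEs at or after it. Neither the table nor its footnotes say which date assigns an AE to a block.

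**The concern.** The only anchor in the rule is a visit that precedes surgery, and both fallbacks are the earliest possible date in the known period. An AE with a partial date in the implant month or year is therefore pulled backwards, possibly across the implant date. Table 14.1.3.2 is the one planned all-cause AE table that separates the two periods. For an implanted device, a surgical-period event displayed as a screening event errs in the unfavourable direction for a safety display.

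The largest day-missing share falls between implant and Day 0. AEs are next collected on schedule at Post-Surgical Clearance, 14 to 21 days after implant, so some onset dates may have to be recalled.

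**Working it through.** The documents give no figure for this point and no count of partial dates, so every share below is conditional on the date being partial.

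**Inputs.** Consent to implant: up to 30 days (Protocol 11.3). Implant to Day 0: 14 to 21 days (Protocol 11.5.1). Day 0 to Week 12: 84 days (Protocol 11.11). The post-implant window is days 0 to 21 + 84 = 105, which is 106 days. Baseline visit is read as the consent date.

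**Assumptions.** Consent is uniform over a calendar year, and AE onset is uniform within each window.

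**1. Check of the coding.** The rules applied literally return the SAP's own examples: XX-Sep-2020 becomes 01-Sep-2020, and XX-XXX-2020 becomes 01-Jan-2020.

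**2. When the completed date precedes implant.** Every consent date from 2021 to 2023 was paired with implant 1 to 30 days later (32,850 pairs).
- Day-missing AE in the implant month: dated before implant in 31,770 / 32,850 = 96.7%. The only exception is implant on the 1st.
- Year-only AE in the implant year: 32,760 / 32,850 = 99.7%. The only exception is implant on 1 January.
- In later months or years the completed date is never before implant.

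Examples:
- Consent 07-Mar-2022, implant 28-Mar-2022: XX-Mar-2022 becomes 07-Mar-2022.
- Consent 21-Feb-2022, implant 14-Mar-2022: XX-Mar-2022 becomes 01-Mar-2022.
- Consent 20-Dec-2022, implant 10-Jan-2023: year-only 2023 becomes 01-Jan-2023.

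**3. Day-missing share over days 0 to 105.** With implant on day j of a month of L days, L − j + 1 window days fall in the implant month, and j = 1 is exempt. Summing over j = 2 to L gives L(L − 1)/2 per month. Over a 365-day year this is 7 × 465 + 4 × 435 + 378 = 5,373, a mean of 5,373 / 365 = 14.72 days. The share is 14.72 / 106 = **0.139**. Simulation of 1,000,000 subjects, with implant 7 to 30 days after consent, gives the same: 0.031 through the baseline clause plus 0.108 through the first-of-month default.

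**4. Year-only share over days 0 to 105.** Window days in the implant year: 260 × 106 + (105 × 106) / 2 = 33,125. Removing the 106 for implant on 1 January leaves 33,019. The share is 33,019 / (365 × 106) = **0.853**.

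**5. By onset period (simulation).**

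| True onset | Day missing | Year only |
|---|---|---|
| Days 0–105 | 0.139 | 0.853 |
| Implant to Day 0 | 0.696 | 0.975 |
| Day 0 to Week 12 | 0.031 | 0.833 |

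Within the first weeks the day-missing share falls from 0.869 (days 0–6) to 0.638 (days 7–13) and 0.409 (days 14–20). If onset is front-loaded (exponential, mean 30 days), the share over days 0–105 is 0.373. A consent-to-implant lag of 1 to 30 days, or fixed at 30, moves the shares by no more than 0.2 percentage points.

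**6. Baseline visit read as Day 0.** Over days 0–105 the shares fall to 0.051 (day missing) and 0.004 (year only).

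**The case against.** **The table may not use the completed date.** SAP 5.1 says summary tables use data from protocol-specified visits as reported in the CRF, and AEs are collected at every visit, so blocks could be assigned by reporting visit. A reader might infer that these AEs would certainly be filed as pre-implant. The documents do not support that: the link rests on the stated purpose of 5.8. It is the natural reading, and no other rule for the split was found, but it remains an inference.

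**Baseline visit may mean Day 0.** SAP 8.4.1 and Table 14.1.2.2 attach the word baseline to Day 0, and in Table 14.1.2.20 the corticosteroid block prints it where the parallel blocks print Day 0. SAP 5.3, Appendix A and Protocol 3 favour Screening. The ambiguity is real: under the Day 0 reading the year-only problem nearly disappears, and the day-missing share falls to about 5%.

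**Partial dates should be few.** Onset is recorded for every AE (Protocol 15.4), data are cleaned (Protocol 18.2.6) and queries are worked before lock (SAP 4.3). This stands. Year-only dates should be rarer still, so their large shares should not be the headline.

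**The remedy reverses the error and does not serve treatment emergence.** Both parts stand. Study stimulation starts at Day 0. For AEs truly starting between Day 0 and Week 12, the share dated before Day 0 is 17% (day missing) and 88% (year only) under both the current rule and an implant floor.

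**Conclusion.** The point holds as a minor one. SAP 5.8 can date a post-implant AE before implant when the day is missing in the implant month, or when only the year is known in the implant year. The consequence for Table 14.1.3.2 depends on the completed date being used there. The size is about 14% of day-missing AEs over days 0 to 105 and 70% between implant and Day 0 if baseline visit means Screening, or about 5% over days 0 to 105 if it means Day 0. These figures rest on uniform consent and onset timing. The absolute number is unknown and probably small.

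A reader might infer lost events or a biased arm comparison; neither follows. SAP 9.1 tabulates AEs from consent to Week 12, so none drops out. The rule is the same in both arms, and implant precedes randomization. Table 14.1.3.1 does not split by implant, Tables 14.1.3.3 to 14.1.3.7 select on relationship, and Listing 16.1.2.7 shows each onset. The long-term SAP (CLP-008, 5.5) borrows the rule, but its Table 14.8.3.2 has no implant split, so no consequence arises there.

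**What to change.** In SAP 5.8:

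1. Name the visit meant by baseline visit.
2. When the known month or year allows onset on or after implant, set AE onset to the later of the Implant Procedure date and the first day of the known period. The exception is a recorded outcome date showing that the event ended before implant: either a complete date, or a partial one whose latest possible date is before implant. In all other cases keep the present defaults.
3. State that Table 14.1.3.2 uses this date.

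**Cost.** SAP wording and one date derivation. No post-implant AE is then dated before implant, but some true screening AEs with partial dates move to the post-implant block: up to about 68% (day missing) and 97% (year only) when no usable outcome date exists. With complete outcome dates and assumed durations of 3, 7 and 14 days, the shares are 18%, 39% and 60% (day missing) and 19%, 45% and 75% (year only). The documents give no durations. If the outcome date is missing to the same degree as the onset, the check excludes nothing and the shares return to 68% and 97%. This direction of error is conservative for safety.

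Do not extend the implant floor to a treatment-emergent flag based on Day 0, because it does not correct dates relative to Day 0. The undefined treatment-emergent term in SAP 9.1 and the year-only medication-start clause, which tests an unknown month, are separate drafting points.

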14 PRIOR AND CONCOMITANT MEDICATION

14.1 Prior RA Medication

Prior use must start from date of RA diagnosis and include all approved for RA biologic and targeted synthetic DMARDs. At a minimum, the year of start and stop must be recorded. The subject's medical record should substantiate the type, dose and duration of usage, as well as reason for stopping.

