5.8.1 Missing data for efficacy and safety endpoints

Missing data for each efficacy endpoint will be handled as described in Sections 8.2, 8.3, 8.4 and 8.6.

For continuous endpoints, change from baseline will be set to missing at visits with missing post-baseline values or where data were imputed to missing. Continuous efficacy endpoints will be set to missing for subjects who received rescue treatment before Week 12.

For binary endpoints, subjects with missing efficacy data, early withdrawals, or subjects who received rescue treatment before Week 12 will be imputed as non-responders and therefore treated as a failure (e.g., no ACR20/50/70 response, DAS28-CRP remission or no moderate/good EULAR response).

Additional rules for handling of missing data and rescue treatments are detailed below:

- *Missing efficacy data.* Visits with missing data (due to a missed visit or missing component of a composite endpoint) will be set to treatment failure.
- *Early withdrawals.* Only visits following the early withdrawal visit will be set to treatment failure.
- *Prednisone equivalent >10 mg/day.* The visit after a period (time from previous visit up to the day before the current visit) of average daily corticosteroid use exceeding 10 mg/day prednisone will be set to treatment failure and continuous endpoints set to missing due to rescue.
- *Corticosteroid injection.* If subject received a corticosteroid injection within 30 days prior to a study visit, that visit will be set to treatment failure and continuous endpoints set to missing due to rescue.
- *b/ts/csDMARD.* Subjects who receive treatment before Week 12 with biologic, targeted synthetic, or additional conventional synthetic DMARD, or increased dose of background

conventional synthetic DMARD will be set to treatment failure at all subsequent visits and continuous endpoints set to missing due to rescue.

- *Missing baseline value.* For efficacy endpoints, a missing value at baseline will not be imputed, and the endpoint will be set to missing for all visits.
- *Missing analytes/ retests.* If an analyte value is missing/its concentration cannot be reliably determined (e.g., sample was lost, damaged, etc.), a retest value will be used for that analyte. If an initial value is non-missing and reliable but the analyte was retested, the value that coincides with the date of clinical assessment will be used. If neither an initial nor retest value is available, the analyte value will be set to missing.

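### Two medication start-date rules in SAP 5.8 can put a DMARD start on the wrong side of consent or Week 12 and so misclassify rescue

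*SAP*

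**What the plan says.** SAP 5.8 gives the purpose of its date rules: "a complete date will be established in order to identify AEs or medication as occurring during treatment or not". For medication starts it has two rules.

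- **Day and month missing.** The condition for using the baseline date is "If baseline visit occurred in the same month in the same year as the occurrence of the medication". Failing that: "Otherwise, the start day and month is set to 01 January". The parallel adverse-event rule compares years only: "If baseline visit occurred in the same year as the occurrence of the AE".
- **Day missing, month known.** The baseline date is used if baseline fell in that month. "Otherwise, the start day is set to the first day of the month".

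For a stop with only the year known: "The stop day and month is set to 31 December". No medication rule refers to Day 0, to the Week 12 visit, or to what was recorded at a visit.

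The dates feed the primary endpoint. SAP 5.8.1 addresses "Subjects who receive treatment before Week 12 with biologic, targeted synthetic, or additional conventional synthetic DMARD", or an increased dose of background therapy, and sets these subjects to treatment failure at all later visits. SAP 8.3.3 counts subjects rescued before Week 12 as ACR20 non-responders. Protocol 14.5 and 17.7 word rescue as initiating a treatment, and the list in Protocol 14.5 speaks of additions and dose increases.

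On the precision of dates, Protocol 14.1 says of prior biologic and targeted synthetic DMARDs: "At a minimum, the year of start and stop must be recorded". Protocol 14.5 has rescue timing recorded on both the follow-up visit and Concomitant Medication CRFs. SAP Table 14.1.2.20 takes it from the start date on the medication log.

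**The concern.** The year-only start rule asks about a month in exactly the case where the month is unknown. Read literally, it always falls through to 01 January. A conventional synthetic DMARD added during the blinded period of the consent year is then dated before consent, where it resembles background therapy, and a real rescue is missed.

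The day-missing rule errs the other way. Protocol 14.5 allows additional RA treatment at any time after the Week 12 assessments, so starts in the following weeks are foreseeable. Moving such a start to the first of its month can place it before the Week 12 visit. A subject who met ACR20 without rescue is then scored as a failure.

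The classification at stake enters the primary endpoint and the four key secondary endpoints, all of which use the same rescue rule.

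**Working it through.** **The plan's own yardsticks.** SAP 3.4 gives a smallest significant difference of 11.2 to 12.8 points for control rates of 20% to 40% with 125 per arm. With the pooled z-test and a critical value of 1.96:

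- Control 25/125: 39/125 gives 0.112 / √(0.256 × 0.744 × 2/125) = 2.03. 38/125 gives 0.104 / √(0.252 × 0.748 × 2/125) = 1.89.
- Control 50/125: 66/125 gives 0.128 / √(0.464 × 0.536 × 2/125) = 2.03. 65/125 gives 0.120 / √(0.46 × 0.54 × 2/125) = 1.90.

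The thresholds are therefore 14 and 16 responders, as stated. The power of 0.773 at 50% versus 30%, which includes the Stage 1 futility stop, was also reproduced: 1,000,000 simulated trials gave 0.773.

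**Year-only start.** Assume consent is uniform over a 365-day year. On the longest nominal timeline (Protocol 11.11), Day 0 is 30 + 21 = 51 days after consent and Week 12 is 84 days later. Take a start k days after Day 0, k = 0 to 83. It is dated before consent if it falls in the consent year and consent was not on 1 January:

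- Share = (365 − 51 − k − 1)/365. At the mean k of 41.5 this is 271.5/365 = 74%.
- With Day 0 at 28 days (assumed), it is (365 − 28 − 41.5 − 1)/365 = 294.5/365 = 81%.
- Under the adverse-event form of the rule (same year) it is 0%.

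Example: consent 15 March 2023, conventional synthetic DMARD added 10 June 2023, only the year recorded. Imputed start: 1 January 2023.

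**Day-missing start after Week 12.** Even with visit windows, Week 12 is at least 14 + 77 = 91 days after consent, so the same-month baseline exception cannot apply. For a start k days after Week 12, the imputed date precedes the visit only if both fall in the same calendar month and the visit was not on the 1st. A month of L days has L − 1 − k such visit dates. Over twelve months, with Week 12 dates uniform:

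- Share = (365 − 12 − 12k)/365 = 1 − 12(1 + k)/365.

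| Start window after Week 12 | Mean k | Share dated before Week 12 |
|---|---|---|
| 0–7 days | 3.5 | 1 − 54/365 = 85% |
| 0–14 days | 7 | 1 − 96/365 = 74% |
| 0–28 days | 14 | 1 − 180/365 = 51% |

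Counting from day 1 instead of day 0 gives 84%, 72% and 49%.

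Example: consent 29 March 2023, Week 12 on 11 August 2023, DMARD started 20 August 2023, day missing. Imputed start: 1 August 2023, before the visit.

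**Scale.** One recoded subject moves an arm by 1/125 = 0.8 points, and only if the subject would otherwise be a responder. The documents give no count of partial dates, so the following is an assumed range. If 2%, 5% or 10% of true responders in both arms were recoded as failures, power at 50% versus 30% would fall from 0.773 to 0.762, 0.742 or 0.709. If recoding occurred in the treatment arm only, it would fall to 0.737, 0.675 or 0.555. If in the control arm only, it would rise to 0.795, 0.825 or 0.866. Nothing in the documents suggests a one-sided pattern.

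**The case against.** The strongest reply is that few dates will be affected. Year-only dates are accepted only for prior biologic and targeted synthetic DMARDs. In-study medication is recorded at every visit, including the Week 13, 14 and 15 titration visits. The Week 12 treatment decision goes on the visit CRF, rescue before Week 12 is a protocol deviation, and queries are worked through before lock. This stands as an argument about frequency. It does not repair the rule, because the SAP nowhere says that CRF-recorded timing overrides an imputed date.

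Existing outputs help only in part. The listing of subjects rescued before Week 12 shows those already classified as rescued; it does not flag imputed dates and cannot show a rescue hidden by 01 January. The rescue sensitivity analysis in SAP 8.3.4 substitutes the ACR20 value from before the intervention. That softens a false rescue, but it takes the rescue timing as given.

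Recoding also matters less than the percentages suggest. Protocol 14.5 ties additional treatment to worsening or inadequate improvement, so many subjects who start a DMARD just after Week 12 will already be non-responders.

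A reader might also infer that the 31 December stop rule turns washed-out DMARDs into rescue. That needs rescue to be derived from overlap of treatment with the study period. The protocol words rescue as initiation, and on that reading a stop date is irrelevant. Taken literally as any treatment before Week 12, the overlap reading would catch nearly every subject, since eligibility requires earlier exposure to a biologic or targeted synthetic DMARD. Washout is also counted in days (Protocol 11.2.2 and Appendix A), so a recent stop recorded by year alone is unlikely.

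**Conclusion.** The point holds for the two start rules. The year-only test is a drafting error that shows on the face of the text. The day-missing rule lacks a bound at Week 12, the boundary on which DMARD rescue status depends. The shares of 74% to 81% for year-only starts and about 74% for day-missing starts within 14 days are conditional on a partial date having occurred and on dates uniform over the year. They are not rates of misclassification in the trial.

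No direction of bias follows: one error hides rescue and the other creates it. A reader might infer a material threat to the primary result. The documents do not support that, because the number of partial dates is unknown and probably small, and each affected subject counts for at most 0.8 points against a threshold of 14 to 16 responders. The stop rule is a problem only if rescue is derived from overlap, which SAP 5.8.1 leaves open by not repeating the protocol's initiation wording. The correction is worth making because it is cheap and because, after unblinding, each such date would be settled with the arm known.

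**What to change.** In SAP 5.8 and 5.8.1:

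1. State that DMARD rescue is derived from initiation, addition or dose increase after consent and before Week 12, consistent with the protocol. This also makes the imputed stop date irrelevant to rescue.
2. Replace the same-month test with a same-year test only for medications recorded as not being taken at consent. Keep medications recorded as prior dated before consent. A bare same-year test would move a genuinely prior start in the consent year to the consent date, and would still date a year-only start after Week 12 in that year before Week 12.
3. Bound every imputed start by the timing recorded on the visit and medication CRFs, so that a drug first recorded as post-Week 12 treatment is never dated before the Week 12 visit.
4. At blinded data review before lock, list the subjects whose rescue status depends on an imputed date. If there are any, repeat the primary analysis with the opposite classification.

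The cost is one SAP paragraph, a short listing and possibly one extra sensitivity run.
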